8.5 ADVERSE EVENTS FOLLOW-UP

It is the Investigator's responsibility to maintain documentation of each reported adverse event. All adverse events will be followed in accordance with applicable licensing requirements. Such documentation will include the following:

- Adverse Event (Diagnosis not symptom)
- Detailed drawings or photographs, when appropriate
- Date and time of onset
- Date and time of resolution
- Adverse event intensity and classification, as applicable
- Treatment regimen instituted, including concomitant medications prescribed, in accordance with applicable licensing requirements
- Any referral to another health care provider if needed
- Outcome, ocular damage (if any)
- Likely etiology.
- Best corrected visual acuity at the discovery of the event and upon conclusion of the event

In addition, if an infiltrate(s) is present, the Investigator will complete the Corneal Infiltrate Assessment Form / eCRF.

Photographs or video recordings may be collected at the Investigator's discretion for purposes of documenting adverse event findings.

Visual acuity (best corrected) should be recorded prior to the report of an adverse event (as part of the Baseline Evaluation), upon the subject's report of the adverse event, and after the adverse event has resolved.

Subjects who present with an adverse event should be followed by the Investigator, within licensure, until all signs and symptoms have returned to pre-treatment status, stabilized, or been satisfactorily resolved. If further treatment (i.e. beyond licensure) is required, the patient will be referred to the appropriate health care provider. The Investigator should use his/her clinical judgment as to whether or not a subject (eye) reporting with an adverse event should continue in the study. If a subject is discontinued from the study, it will be the responsibility of the Investigator to record the reason for discontinuation. The investigator will also complete the Adverse Event Classification (AEC) Outcome form / eCRF. Any subjects with ongoing adverse events related to the test article as of the final study visit date should be followed to resolution of the adverse event or until referral to an appropriate health care provider, as recommended by the Investigator.

9.1 STATISTICAL METHODS TO BE EMPLOYED

This method is a general outline of the statistical methods that will be implemented in this clinical trial. For more details, refer to the stand-alone Statistical Analysis Plan (SAP) of this clinical study.

Cohort Populations:

CR-5816 Protocol v7.0, Amendment 6.0

- The analysis population will include subjects who have successfully completed all study visits without a protocol deviation documented as impacting the unbiased assessment of the hypotheses
- The safety population will include all randomized subjects who have successfully tried at least one study lens

Statistical Considerations:

Statistical programming and analyses will be performed using SAS (SAS Institute, Cary, NC) version 9.4 or higher. Throughout the analysis of the data, the results of each eye will be used when available for summarization and statistical analysis.

Summary tables (Descriptive statistics and/or frequency tables) will be reported at baseline and each post fit time period for all efficacy and safety variables for each subject/eye by study lens type (as appropriate) for both the completed and discontinued subjects. Continuous variables will be summarized with descriptive statistics (number non-missing (n), mean, standard deviation (SD), median, minimum and maximum). Frequency count and percentage of subjects or eyes within each category will be provided for categorical data. Unscheduled visits will be summarized separately if applicable.

Summaries will be presented by study article type (Test OR Control). The denominator for percentages of counts will be the same for each visit on the summary tables and will equal the final number of subjects or eyes in the group under consideration. Unscheduled visits will be summarized separately and excluded from the analysis.

Analysis Population Sets:

Primary and secondary analyses will be performed on all randomized subjects who completed the study and did not substantially deviate from the protocol as determined by the trial cohort review committee prior to database hard lock (Per-protocol population). Justification for excluding subjects with protocol deviations will be documented in a memo to file.

Primary Analysis:

CLUE Comfort scores will be analyzed using a Bayesian hierarchical model to compare between test and control lenses. The regression model will include baseline values, lens type, lens wearing sequence, lens wearing period. Subject will be included in the regression model as random effects factors. Non-informative prior distributions will be used for coefficients in the models as well as for the error terms. The Metropolis sampler algorithm as implemented in the SAS MCMC Procedure will be used to carry out parameter estimation. Results will be reported as regression coefficient mean estimates with credible intervals over all time points and within each timepoint. The null and alternative hypotheses for non-inferiority are as follows: $H_0: \mu_t - \mu_c \leq -5$, $H_a: \mu_t - \mu_c > -5$ where μ_t and μ_c are the comfort score mean of Test and Control lenses respectively. Non-inferiority will be declared if the lower bound of the credible interval of the mean difference between Test and Control is greater than -5. If non-inferiority is demonstrated, superiority will then be tested and can be used for any claim substantiation. Superiority will be concluded if the lower credible interval limit is above zero (0).

Secondary Analysis

Comfort at the end of the day [REDACTED] will be analyzed independently using Bayesian Multinomial models for ordinal data. Lens type, lens wearing sequence, lens wearing period will be included in each regression model as fixed effects; and subject as random factors. Independent vague prior distributions will be used for the coefficients in the models as well as for the error terms. The Metropolis sampler algorithm as implemented in the SAS MCMC Procedure will be used to carry out parameter estimation. Results will be reported as regression coefficient mean estimates and odds ratios with credible intervals. For each item, the null and alternative hypotheses for non-inferiority are as follows: $H_0: OR \leq 0.67$ $H_a: OR > 0.67$; where OR represents the odds ratio of having positive experience wearing the Test lens compared to the Control lens. For each endpoint, non-inferiority will be declared if the lower bound of the credible interval of OR is greater than 0.67. If non-inferiority is demonstrated, superiority will then be tested and can be used for any claim substantiation. Superiority will be concluded if the lower credible interval limit is above one (1). For further details and analyses of other endpoints please see the statistical analysis plan.

A post-hoc statistical analysis plan may be considered if necessary but only at the discretion of the Study Responsible Clinician and Study Biostatistician.

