4.1 PRIMARY AND SECONDARY ENDPOINTS

The primary endpoint of this study is the assessment of overall CLUE comfort in heavy digital device users at follow-up. All hypotheses are exploratory in nature.

The secondary endpoints of this study include (1) measurements of time to haze (TTH), (2) Average wear time and comfortable wear time, (3) CLUE lens handling in heavy digital device users at follow-up, (4) Comfort at the end of the day [REDACTED] and (5) Difference between total time of device use and comfortable wear time on a typical day.

TTH is a metric that has been developed at the CCLR in order to measure the maximum time a CL wearer can keep their eye open without their vision becoming hazy; it is a measure of how the drying of the CL surface with open eyes affects vision. [REDACTED]

Subjective assessments of comfort and handling will be performed using the Contact Lens User Experience™ (CLUE™) questionnaire. CLUE is a validated patient-reported outcomes (PRO) questionnaire to assess patient-experience attributes of soft contact lenses (comfort, vision, handling, and packaging) in a contact-lens wearing population in the US, ages 18-65. Derived CLUE scores using Item Response Theory (IRT) follow a normal distribution with a population average score of 60 (SD 20), where higher scores indicate a more favorable/positive response with a range of 0-120. A 5 point increase in an average CLUE score translates into 10% shift in the distribution of scores for population of soft disposable contact lens wearers.

Other Observations	
1	Keeping your eyes from feeling dry at the end of the day [REDACTED]
2	Clarity of vision at the end of the day (Item ID P3_0006_p07)
3	CLDEQ8
4	Near Contrast Sensitivity
5	CLUE™ Comfort and Comfort at the end of the day [REDACTED] of ACUVUE OASYS® throughout the 4-week wear period (dispense 1, 2-week follow-up 1, dispense 2, 2-week follow-up 2).

Primary Hypothesis:

The overall CLUE comfort score of the ACUVUE OASYS® test lens will be non-inferior to the ULTRA™ control lens in adapted SCL wearers (i.e. at least 5 days/week and 8 hours/day wear) who use digital devices for at least 8 hours a day over the 4 weeks wear period.

Secondary Hypotheses:

- ACUVUE OASYS® test lens will be statistically non-inferior to the control lens ULTRA™ with regards to time to haze (TTH) over the 4 weeks wear period using a non-inferiority margin of 2 seconds.

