14	Efron Biomicroscopy	The Efron slit lamp classification scale will be used to grade the findings. This includes corneal and conjunctival staining measurements with fluorescein (Section 16.2).	Biomicroscopy
15	Eye Rinse (if applicable)	The study investigator or technician will rinse the subject's eyes thoroughly with saline if the subject would like to wear their study CL before leaving the CCLR.	Eye Rinse
16	Exit logMAR Visual Acuity	Distance visual acuity will be measured for each eye with the subject's spectacle correction or study lenses in place. The acuity will be recorded to the nearest letter OD, OS, and OU (Section 16.2).	Exit Visual Acuity
17	Subject Instructions	Subjects will be instructed: 
 to wear their study lenses for a minimum of 5 days/week for 8 hours/day, while using digital devices. to only use the provided study lenses and study solution (habitual spectacle use is permitted, but no other lens brand/kind). to attend the Day 14 follow-up visit with their study lenses, having worn them for at least 6 hours while using digital devices. 	Instructions

Visit 4: Treatment 1 – Day 14 Follow-Up

VISIT 4: Treatment 1 – Day 14 Follow-Up			
Step	Descriptor	Details	CRF
		The subject attends the visit wearing the study CLs, after having worn them for at least 6 hours while using digital devices.	

1	Changes in Concomitant Medications, Medical History and Adverse Events	Record any changes in concomitant medications and any adverse events that may have occurred since the last scheduled study visit.	Concomitant Medications Medical History Adverse Events (if applicable)
2	Subject Wear Time	Average wear time and comfortable wear time with the study lenses will be recorded.	Wear Time
3	Compliance	Subject compliance with wearing the study lenses will be recorded.	Compliance
4	Subject Reported Digital Device Use (Study Lens 1)	Subjects answer questions about their digital device use (duration while using digital devices, purpose etc.).	Subject Reported Digital Device Use
5	CLDEQ 8, MRD & CLUE questionnaires	The subject will complete the CLDEQ8, MRD and CLUE questionnaire using the BioClinica kiosk to evaluate the study lenses while using digital devices (Section 16.1).	Questionnaire
6	Unscheduled Lens Replacements	Any unscheduled lens replacements will be recorded (e.g. if subject tears lens while insert and more than two lenses are used/day as a result).	Unscheduled Lens Replacement

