9.6 PROCEDURE FOR REPORTING DEVIATIONS FROM STATISTICAL PLAN

The analysis will be conducted according to section 9.1. There are no known reasons for which it is planned to deviate from these analysis methods. If for any reason a change is made, the change will be documented in the study report along with a justification for the change.

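### The superiority conclusion that section 9.1 allows for claims rests on completers only; follow-up comfort ratings from subjects who left enter no test

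*Protocol*

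**What the plan says.** Section 9.1 (Analysis Population Sets) fixes the population for every test: "Primary and secondary analyses will be performed on all randomized subjects who completed the study and did not substantially deviate from the protocol". The only other population in 9.1 is the safety population. Discontinued subjects enter the efficacy reporting only through summary tables, which are produced "for both the completed and discontinued subjects".

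The Primary Analysis part of 9.1 then adds a second step: "If non-inferiority is demonstrated, superiority will then be tested and can be used for any claim substantiation". For CLUE comfort the criterion is a lower credible limit above 0. For comfort at the end of the day it is an odds-ratio limit above 1, with the same permission for claims. Neither step names a different population, and 9.6 confirms: "The analysis will be conducted according to section 9.1".

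Section 4.1 defines the outcome: "The primary endpoint of this study is the assessment of overall CLUE comfort in heavy digital device users at follow-up". It also says: "All hypotheses are exploratory in nature".

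**The concern.** For non-inferiority, dropping non-completers and serious deviators is usual, and it is not criticised here. Superiority is different. Membership of the completer set is decided after randomisation, by events the lens itself may cause, so restricting the test to that set is not conservative.

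Two such exits are written into the protocol. An unacceptable fit at a follow-up visit ends participation (4.7.1, for example Visit 4 step 9). An investigator may also stop treatment for an adverse event (5.1), and the synopsis explains the 250-subject maximum by adverse-event discontinuations seen in phase 1.

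The discarded information can exist. At Visit 4 step 5, before the fit check, the protocol states: "The subject will complete the CLDEQ8, MRD and CLUE questionnaire using the BioClinica kiosk to evaluate the study lenses while using digital devices". A subject removed at step 9 has therefore just rated that lens after wear, and 9.1 uses the rating in no test. If one lens loses more wearers who rated it low, it looks better among those who remain. At stake is a false superiority claim at the final analysis; the interim look is already past (9.4).

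**Working it through.** The protocol gives no figure to reproduce here. It states neither loss after randomisation nor exits by lens. The ratio of 135 enrolled to 80 completers cannot serve as dropout, because under 9.7 enrolled subjects include those never randomised. The size below is therefore an illustration.

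**Inputs from the protocol**
- Completers: 80 (phase 1 target) + 50 (phase 2) = 130 (9.2, 9.4).
- Population SD of CLUE: 20 (4.1).
- Two-sided 5% (9.3), that is 2.5% one-sided.

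**Assumed inputs**
- Within-subject correlation 0.5, so the SD of the paired difference is 20 × √(2 × (1 − 0.5)) = 20. SDs of 15 and 25 are also shown.
- Lens-related loss after randomisation L = 10% or 20%.
- Leavers rate the lens they left on D = 10 or 20 points lower.
- Share of exits on the test lens s = 0.65 or 0.75.
- A single look; the interim rule is not modelled.

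**Shift among completers.** Including leavers lowers the test mean by D × L × s and the control mean by D × L × (1 − s). If the true difference in all randomised subjects is 0, completers show

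shift = D × L × (2s − 1).

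| D | L | s = 0.65 | s = 0.75 |
|---|---|---|---|
| 10 | 10% | +0.3 | +0.5 |
| 10 | 20% | +0.6 | +1.0 |
| 20 | 10% | +0.6 | +1.0 |
| 20 | 20% | +1.2 | +2.0 |

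**False superiority** = 1 − Φ(1.96 − shift/SE), with SE = SD/√130. For SD 20, SE = 20/11.40 = 1.75.

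| Shift | SD 15 | SD 20 | SD 25 |
|---|---|---|---|
| 0 | 2.5% | 2.5% | 2.5% |
| +0.3 | 4.2% | 3.7% | 3.4% |
| +0.6 | 6.6% | 5.3% | 4.6% |
| +1.0 | 11.5% | 8.2% | 6.6% |
| +1.2 | 14.7% | 10.1% | 7.9% |
| +2.0 | 33.0% | 20.6% | 14.7% |

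With s = 0.5 the shift is 0. If the same exits fall on the control lens, the sign reverses: at SD 20, 1.7% at −0.3 and 0.1% at −2.0.

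**What using the observed ratings recovers.** Simulated trials (4,000 per setting, 144 or 162 randomised for about 130 completers) used a random-subject model with lens, period and sequence. Period 1 leavers never rate the second lens, and 100% to 50% of leavers have a follow-up rating of the lens they left on.
- L = 10%, s = 0.65, D = 20: the shift falls from 0.6 in completers to 0.2–0.4 in the added analysis. False superiority is 5.5% per-protocol and 2.9–3.9% when both analyses must succeed.
- L = 20%, s = 0.75, D = 20: the shift falls from 2.0 to 0.5–1.2, and false superiority from 20.6% to 5.0–9.7%.
- Power at a true +5 points with 20% exits unrelated to comfort: 81.6% per-protocol, 79.5–80.1% with both required.

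**A different leaving mechanism.** Here 160 subjects are randomised, the correlation is 0.3 to 0.7, and a subject leaves when the rating of the worn lens falls below a cut-off. With equal cut-offs for the two lenses there was no bias (2.3–2.6%). With a higher cut-off on the test lens (13.5–23% leaving), the completer bias was +0.5 to +2.2 points and false superiority 6.1–22.9%. Using all observed ratings gave 2.1–3.0%. Recovery is nearly complete in this case because leaving depends only on a rating that was recorded.

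**The case against.** The strongest reply is that 9.1 calls itself an outline and defers to the SAP, which was not available for this review and may contain an all-randomised analysis. It could be added that the hypotheses are non-inferiority and exploratory, that 9.5 asks for the missingness mechanism to be considered, and that nothing shows exits differing by lens or related to comfort. Fit failure is judged on coverage, edge lift and movement, not on comfort.

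Part of this stands. Differential loss is not documented, every input to the size is assumed, and 20.6% is an extreme corner. The remedy also depends on leavers having been rated. Exits at unscheduled visits may carry no CLUE (6.3), and fit failures at dispensing come before any follow-up rating of that lens. In the worst setting, if only 25% of leavers were rated, requiring both analyses still leaves about 14% false superiority.

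The rest does not stand. The population is not left open: 9.1 states it for all primary and secondary analyses and draws the claim-bearing superiority conclusion from them. Section 9.5 raises the issue but prescribes no analysis, and 9.6 only requires that changes be documented. The exploratory label sits beside a study typed in the synopsis as a claims study, with superiority expressly usable for claims.

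**Conclusion.** The point holds, limited to the final superiority step. As written, a superiority claim would rest only on subjects who completed without substantial deviation, although some who left will have rated the lens after wear. Neither the direction nor the size of any bias can be read from the protocol. With balanced exits there is none, and with exits leaning to the control lens the test is conservative for the test lens. Under the assumed exits leaning to the test lens, false superiority is 3.7% to 20.6% at an SD of 20, against a nominal 2.5%. That range rests on the assumed loss, split, deficit and correlation, and on a single look. The non-inferiority analysis is not affected by this point. The weakness is worth correcting because the remedy is cheap, not because bias has been shown.

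**What to change.** In 9.1, keep the per-protocol set for non-inferiority. Add that, for any superiority conclusion, the same random-subject model is also run on all randomised subjects dispensed at least one study lens. It should use their observed CLUE ratings under the lens worn, at the same follow-up time points as the per-protocol analysis. Ratings taken just after insertion (Visits 2 and 6 step 12, Visits 4 and 8 step 17) should be left out, because they do not reflect wear. Superiority is claimed only if this analysis also meets the criterion: lower credible limit above 0 for CLUE, or above 1 for the odds ratio, where the end-of-day comfort item replaces CLUE.

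The cost is one paragraph and one more model run on data already collected. The estimate may be less favourable, power drops slightly, and bias is recovered only in part. The added condition can only make a claim harder to reach. It does come after the interim analysis (9.4), so it must be documented as such and the operating characteristics referred to in 9.3 rechecked.

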- ACUVUE OASYS® test lens will be non-inferior to the ULTRA™ control lens with regards to comfortable wear time and Average wear time over the 4 weeks lens period using a non-inferiority margin of 2 hours.
- In terms of Difference between total time of device use and comfortable wear time on a typical day, the test lens ACUVUE OASYS® will be non-inferior to the control lens ULTRA™ over the 4 weeks lens wear period using a non-inferiority margin of -2 hours.
- ACUVUE OASYS® test lens will be non-inferior to the ULTRA™ control lens with regards to lens handling over the 4 weeks lens wear period.
- ACUVUE OASYS® test lens will be non-inferior to the ULTRA™ control lens with regards to Comfort at the end of the day [REDACTED] over the 4 weeks lens period using a non-inferiority margin of 0.67 Odds ratio.

Tertiary Hypotheses:

- The overall comfort of the test lens will be non-inferior to the control lens for CLUE comfort in at least one of the study time points (2-week and 4-week).

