9.3 LEVEL OF STATISTICAL SIGNIFICANCE

Unless otherwise specified, all planned analysis for this study will be conducted with a two-sided type 1 error rate of 5%. See CR-5816 Statistical Analysis Plan document for more details on the operating characteristics of this adaptive trial.

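### Section 9.1 names subject as the only random effect for CLUE comfort; if the repeated ratings on each lens enter singly, the pooled interval that decides −5 and 0 is too narrow

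*Protocol*

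**What the plan says.** Section 9.1 of the protocol gives the fixed part of the primary model as "The regression model will include baseline values, lens type, lens wearing sequence, lens wearing period", and the random part as "Subject will be included in the regression model as random effects factors". Priors are non-informative. On output it says: "Results will be reported as regression coefficient mean estimates with credible intervals over all time points and within each timepoint". Non-inferiority is declared if the lower credible limit for test minus control exceeds −5. Superiority, which may then support a claim, is declared if that limit exceeds 0. Section 9.3 sets a two-sided type 1 error of 5%. No credible level is given.

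CLUE is completed repeatedly on each lens (4.4.1 and 4.7.1): at dispensing, Day 1, Day 14 and Day 28. At Day 14 it is completed twice, before lens removal (Visits 4/8, step 5) and after reinsertion (step 17). Section 4.1 places the primary endpoint at follow-up, and its tertiary hypothesis names the 2-week and 4-week time points.

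On the standing of 9.1, the section introduces itself thus: "This method is a general outline of the statistical methods that will be implemented in this clinical trial", and refers to the SAP for detail. Section 9.6, however, says: "The analysis will be conducted according to section 9.1", and adds that no departure is foreseen.

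**The concern.** In a 2x2 crossover a subject intercept removes only what is common to both lenses. A subject who does unusually well or badly on one lens, or in one period, carries that deviation into every rating made on it. The deviation does not cancel in the lens difference, and it does not average out over visits. A model with a subject intercept and independent errors treats m ratings on a lens as m separate pieces of information about the lens effect, so its pooled interval is too short whenever such deviations exist.

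Both primary decisions are read from the lower limit of that interval. Section 4.1 does say: "All hypotheses are exploratory in nature". But the synopsis describes the trial as a clinical claims study, and 9.1 allows a superiority finding to support claims, so the error rate of the rule matters.

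**Working it through.** **Inputs from the protocol.** Subject is the only random effect (9.1). The limits are −5 and 0 (9.1). Two-sided error is 5% (9.3). m = 2 ratings per lens at the named 2-week and 4-week time points (4.1), or m = 3 if Day 1 is pooled as well. Completers number about 80, plus 50 more after the interim analysis, or about 130 (9.2, 9.4).

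**Assumptions.** The interval is 95%, so 2.5% at the lower limit. Ratings enter singly, with independent errors given subject. f is the subject-by-period share of the within-subject variance; the protocol gives no variance split, so a range is shown. In this design subject-by-lens and subject-by-period variation cannot be told apart, so f covers both.

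**Formulas.** Scale the within-subject variance to 1, with f for subject-by-period and 1 − f residual.

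- True variance of one subject's lens difference: 2[f + (1 − f)/m].
- Variance the intercept-only model uses: 2[(1 − f) + f·m/(2m − 1)]/m. It pools about n degrees of freedom that contain the subject-by-period component with 2n(m − 1) that do not.
- One-sided error: 1 − Φ(1.96 / SE ratio), where the SE ratio is the square root of true over model variance.

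**Results for m = 2.** The first row reproduces the intended level.

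| f | true variance | model variance | variance ratio | SE ratio | one-sided error | coverage |
|---|---|---|---|---|---|---|
| 0 | 1.00 | 1.000 | 1.00 | 1.00 | 2.5% | 95.0% |
| 0.05 | 1.05 | 0.983 | 1.07 | 1.03 | 2.9% | 94.2% |
| 0.10 | 1.10 | 0.967 | 1.14 | 1.07 | 3.3% | 93.4% |
| 0.20 | 1.20 | 0.933 | 1.29 | 1.13 | 4.2% | 91.6% |
| 0.50 | 1.50 | 0.833 | 1.80 | 1.34 | 7.2% | 85.6% |

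Worked line, f = 0.20: true 2(0.2 + 0.4) = 1.20; model 0.8 + 0.2·2/3 = 0.933; ratio 1.286; SE ratio 1.134; 1.96/1.134 = 1.73; one-sided error 4.2%.

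**If Day 1 is also pooled (m = 3).** Variance ratios are 1.25, 1.52 and 2.50 at f = 0.10, 0.20 and 0.50, and the errors are 4.0%, 5.6% and 10.8%.

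**Simulation.** 20,000 crossovers per setting, true difference −5, t intervals standing in for vague-prior credible intervals. With m = 2 and f = 0, 0.10, 0.20, 0.50, false non-inferiority was 2.4%, 3.4%, 4.2% and 7.0% at 80 completers, and 2.7%, 3.1%, 4.2% and 7.3% at 130. One mean per subject and period gave 2.4% to 2.8% in these settings. Sample size cancels from the variance ratio, which is why the extension makes no difference.

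**Mixed-model check.** 400 random-intercept fits with baseline, sequence, period and lens (80 subjects, m = 3, subject-by-period SD 8.5 and residual SD 12, both assumed): the lens estimate had an empirical SD of 1.67 against a mean model SE of 1.25. With no subject-by-period variation the two were 1.15 and 1.09.

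**The case against.** The strongest reply is that this is SAP material. Section 9.1 calls itself an outline, points to the SAP, and 9.3 sends the operating characteristics there. The list of terms contains no visit effect, so it fits an analysis of one value per subject and period at least as well as one of single ratings, and on that reading nothing is wrong. Much of this stands: the protocol does not show that the analysis as run will be miscalibrated, and a reader who infers that goes beyond the text. What remains is that 9.1 is not silent. It names a random-effects structure, and 9.6 binds the analysis to it. As written, it admits a version that does not hold the stated error.

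The size also rests on an assumed f. At 5% to 10% the excess is small (2.9% to 3.3%); 7.2% needs a share of one half.

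Three stronger readings are not supported. A reader might infer that the listed model cannot give the promised results within each time point, but separate fits per time point would give them, with one rating per lens. A reader might infer that the missing visit term causes the narrowing. It does not: in a simulation with a common visit shift at f = 0.20, the error was 3.8% without that term and 4.1% with it. A reader might also infer that the second Day 14 rating, where a fresh test pair is set against a worn control pair, is part of the primary contrast. Section 4.1 points the other way: it refers to follow-up, names 2 and 4 weeks, and lists the second dispensing of the test lens separately under Other Observation 5.

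**Conclusion.** The point holds conditionally. Section 9.1 states a random-effects structure that is adequate for one value per subject and period but not for single repeated ratings, and it does not say which is used. If ratings enter singly with independent errors, the pooled lower limit is anti-conservative for both −5 and 0: 3.3%, 4.2% or 7.2% against 2.5% at an assumed share of 10%, 20% or 50% with two ratings, and exactly 2.5% at zero. The additional 50 completers do not change this. It should be fixed because the limit carries both primary decisions and the remedy is cheap. It does not show that the trial's result is wrong, since the SAP may already average the ratings or model the correlation.

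**What to change.** In 9.1, do one of the following for the pooled contrast:

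- add a subject-by-period (equivalently subject-by-lens) random effect, or an equivalent within-period error covariance; or
- state that one mean score per subject and period is analysed.

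Name the ratings that are pooled: Day 14 before lens removal (Visits 4/8, step 5) and Day 28 (Visits 5/9, step 6). State whether Day 1 is included, and that the Day 14 rating after reinsertion is kept for Other Observation 5. If the SAP already says this, one matching sentence in 9.1 is enough.

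Section 9.4 reports that the phase 1 data have been analysed and the extension chosen on predictive probability. The amendment and study report should therefore record that the change followed that look, and say whether the predictive probability used the listed model.

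The cost is wording and a few lines of code, with no new data. The price is a wider interval if single ratings were intended: with two ratings, about 1.07, 1.13 or 1.34 times as wide at f of 10%, 20% or 50%. The protocol states no power. As an illustration only, a nominal 80% computed from the narrower interval would really be Φ(2.80/SE ratio − 1.96), about 75%, 70% or 55%.

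As a separate wording correction that does not affect the interval, 7.1 cites a CLUE rating at a spectacle baseline. None is scheduled: Visit 1 rates the habitual lenses and Visit 2 the study lenses.
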